Protocol # 64989743

Principal Investigator: [name], D.O., FAOCO

Sub investigator: N/A

Site: Private Practice and Research Center

Surgery Center: Tinley Woods Surgery Center

Measurements: [name] Eye Care @ Laser and Cataract Institute, [name]

Post Operative visits: [name] Eye Care @ Laser and Cataract Institute, [name] and [name]

Background: Cataract surgery is projected to be the most commonly performed surgical procedure over the next 10-15 years. Patient expectations of good visual outcomes have risen with the increase in the advancing technology being offered. Cataract surgeons are in need of a clear and consistent process in order to deliver the best possible outcomes with the least amount of error.

Rationale: Biometry data and accurate intraocular lens (IOL) calculations are arguably the most important steps in achieving the desired refractive outcomes. There is limited evidence comparing the two biometers, Zeiss IOL Master 700 to Alcons Argos.

Randomized Observational Prospective Trial:

Hypothesis: The Alcon Argos Biometer's measurements, when used in conjunction with the Barrett Universal II formula, will provide statistically non-inferior outcomes (Mean Absolute Prediction Error of Predicted Spherical Equivalents), when compared to the IOL Master 700 utilizing the (PCA) with the Barrett Universal II (TK) Formula for IOL power calculations.

Primary Objective: To assess if the Alcon Argos Biometer utilizing the Barrett Universal II formula for IOL calculations can give a non-inferior outcome when compared to the Zeiss IOL master 700 utilizing the (PCA) with the Barrett Universal II (TK) formula, when comparing the (mean absolute prediction error of the predicted target spherical equivalencies).

Primary End Point: Mean Absolute Prediction Error (MAPE) of predicted spherical equivalents per biometer. (The absolute value of the difference between the Predicted Post-OP MRSE to the Actual Achieved Post-OP MRSE for the IOL implanted). 2 biometers (Argos and IOL Master 700). Primary End Point (MAPE) will be based on the manifest refraction SE obtained at the postoperative visit day 30 (- 2/+14 days).

Secondary End Points:

a) Percentage of eyes with an Absolute Prediction Error of Predicted SE < or = to (0.5D) with Argos vs IOL Master 700

Protocol # 64989743

b) Median Absolute Prediction Error of Predicted Spherical Equivalents per biometer

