(The absolute value of the difference between the Predicted Post Op MRSE to the actual achieved Post Op MRSE for the IOL implanted) Secondary end points will be based on manifest refraction SE obtained at the postoperative visit day 30 (-2/+14 days)

Exploratory End Points:

a) Percentage of eyes with an Absolute Prediction Error of Predicted SE < or = to (0.25D) with Argos vs IOL Master 700

Safety: All subjects enrolled in the study will be evaluated for safety.

Proposed Method: To enroll approximately 80 patients, 80 right eyes in a randomized observational prospective study over the course of approximately 4 months (8.5 month estimated total study time), randomizing the patients into one of two arms.

Two Arms: All scanned by the same technician (Over 2000 scans a year experience)

A. ARGOS, IOL Master 700, 40 patients, 40 right eyes

B. IOL Master 700, ARGOS, 40 patients, 40 right eyes

Randomization of the actual order for biometry measurements will occur utilizing a randomization program, with blocking on every 2 or 4 subjects.

Rationale: Two arms ensure we eliminate dry eye or fatigue bias for each biometer reading by randomizing the order of the preoperative biometry measurements. In between measurements patient will take a timed 2 min break. No drops will be given prior to measurements, no physical contact with the eye will occur prior to any measurements. This will allow for the most accurate keratometry readings.

Barrett Universal Formula II "K" and (TK) are now considered the gold standard in biometry formulas.

The Barrett Universal II Formula "K" Is available on both biometers, while the Barrett Universal II (TK) is only available on the Zeiss IOL Master 700 biometer.

Surgeon will have access to all biometry readings prior to surgery and at the time of surgery. Surgeon will make the lens selection by choosing the IOL (Intraocular lens) power closest to plano for all biometers involved. If the two IOL diopter powers are not in consensus, the surgeon will utilize the Argos Biometer for the selection.

We will utilize the Barrett Universal II "K" formula for the Argos, and the Barrett Universal II (TK) for the IOL Master 700 to compare the mean absolute prediction error for the predicted spherical equivalents by back calculating.

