Utilizing the Barrett Universal II (TK) (Anterior and Posterior corneal measurements) available only on the IOL Master 700 and comparing it to the Barrett Universal II "K" on the Alcon Argos biometer will allow us to assess if K measurements give non inferior outcomes to the TK Formula.

The Barrett Universal 2 formula uses a theoretical model eye in which anterior chamber depth (ACD) is related to axial length (AL) and keratometry. A relationship between the A-constant and a "lens factor" is also used to determine ACD.¹ The important difference between

Protocol # 64989743

the Barrett formula and other formulas is that the location of the principle plane of refraction of the IOL is retained as a relevant variable in the formula. (1)

1. An improved universal theoretical formula for intraocular lens power prediction. Barrett GD. J Cataract Refract Surg. 1993 Nov;19(6):713-20.

Surgery: Surgery will be performed by 1 surgeon, who routinely performs over 20-25 cases weekly. Optimized lens settings will be used for each biometer.

Corneal Incision size: 2.4 mm Alcon Dual Bevel Blade (Temporal)

Capsulorhexis: Intended size of 4.8mm to 5.2 mm

Phaco: Alcon Centurion

Lens: Alcon IQ Acrysof SN60WF only

Complications: All subjects with any surgical complications will be excluded.

Exclusion Criteria:

Axial Length < 22.00 and > 26.00

Corneal Astigmatism > +1.00 Diopters

CCTS: < 490 and > 600

Prior Refractive Surgery: RK, PRK, LASIK, INTACTS

History of contact lens use: Soft lenses within 2 months of surgery, RGP within 60 months of surgery

Corneal Disease: Keratoconus, Corneal Dystrophies, Any prior corneal Surgery, Prior infections

Retinal Disease: Macular Pathology, CSCR, CME, Macular Degeneration, Drusen, Retinal Detachment, TPPV, SB, prior IVT, Prior PRP or Focal Laser, Diabetic Retinopathy

History of Uveitis

POAG: Undergoing any concomitant MIGS procedure- iStent, Omni, iTrack, Hydrus, etc

Enrollment in any prior clinical trial within 2 years

Systemic Disease that in the investigator's opinion may affect outcome

Currently Pregnant or Breastfeeding

Severe Dry Eye

Tear Osmolarity > 320mOsms/L (Moderate)

Any Surgical Complication(s)

IOL implanted outside of the capsular bag /capsular damage /weakness /CTR placement

Protocol # 64989743

Inclusion Criteria:

Age: 50-85 years old

Clinically Significant Cataracts that interfere with daily activities

Patient is able to understand and able to consent to informed consent

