IAO/COS Illinois Academy of Ophthalmology, Chicago Ophthalmic Society (if not restricted) and/ or

AOCOO-HNS: American Osteopathic College of Ophthalmology- Annual meeting (if not restricted)

Planned Publication:

Peer Reviewed Journal: ASCRS- Journal of Cataract and Refractive Surgery or

AAO- Journal of Ophthalmology

Protocol # 64989743

Sample size and statistical analysis:

For this test, a sample size of approximately 70 will provide acceptable power. Up to 10 more subjects will be enrolled to account for dropouts.

The endpoint is based on the absolute deviation from target MRSE measured by two biometers in the same subject. The difference is calculated for each subject where the Alcon biometer absolute error is subtracted from the XYZ biometer absolute error. A value of zero will reflect no difference, where a negative difference indicates that the Alcon biometer has greater error.

We expect the difference to be zero, however, for safety, knowing that the difference can fluctuate around zero, we set this at -1/20 D. In other words, we assume that the Alcon will, on average, have 0.05D more absolute error.

We set power at 90%. We use a one-tailed alpha of 0.025. The standard deviation if the difference in the two biometers is assumed to be 0.5 D and the NI Delta is set at 0.25 D. These settings and assumptions result in a required sample size of 68 subjects. SAS proc power output is provided:

Fixed Scenario Elements

Distribution	Normal
Method	Exact
Lower Equivalence Bound	-0.25
Upper Equivalence Bound	9999
Alpha	0.025
Mean	-0.05
Standard Deviation	0.5
Nominal Power	0.9

Computed N Total

Actual	N
Power	Total
0.902	68

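### Does the unexplained 0.25 D non-inferiority margin call for a change to the plan?

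*Combined protocol and SAP*

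**What the plan says.** The primary comparison is paired. For each subject the Argos absolute prediction error is subtracted from the other biometer's, so a negative mean difference counts against Argos. Under Sample size and statistical analysis the SD "is assumed to be 0.5 D and the NI Delta is set at 0.25 D"; the SAS output repeats the margin as a lower bound of -0.25. The planning mean does get a reason: "knowing that the difference can fluctuate around zero, we set this at -1/20 D", that is, "we assume that the Alcon will, on average, have 0.05D more absolute error". With one-sided alpha of 0.025 and 90% power, the stated requirement is 68 subjects (actual power 0.902). The plan aims for about 70, plus up to 10 for dropouts.

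The Rationale in the opening section says: "There is limited evidence comparing the two biometers, Zeiss IOL Master 700 to Alcons Argos". Secondary endpoint (a) is "Percentage of eyes with an Absolute Prediction Error of Predicted SE < or = to (0.5D) with Argos vs IOL Master 700", and the exploratory endpoint is the same share at 0.25 D. Neither has an expected rate, and the text links neither to the margin.

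**The concern.** A non-inferiority claim means only that deficits larger than the margin have been excluded, so everything depends on whether a deficit just under the margin is tolerable. Here the planning mean is explained and the margin is not. There is no expected comparator error to set it against, and the plan itself says the comparative evidence is thin. Against a comparator mean absolute error (MAE) of 0.25 D, for example, the margin would allow the error to double. On the trial's own 0.5 D endpoint, that could amount to tens of eyes per 100. The SD of 0.5 D has no stated source either.

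**Working it through.** **Reproducing the plan.** Inputs from the sample size section: margin 0.25 D, mean -0.05 D, SD 0.5 D, one-sided alpha 0.025, power 0.90. The distance to the margin is 0.25 - 0.05 = 0.20 D. The normal approximation gives n = ((1.960 + 1.282) × 0.5 / 0.20)² ≈ 65.7, so 66. The exact noncentral-t calculation gives power 0.897 at n = 67 and 0.9016 at n = 68. The stated 68 and 0.902 are confirmed; 70 eyes give 0.910.

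**What passes.** The half-width of the one-sided 97.5% bound is t × SD / √n. At n = 68 it is 1.996 × 0.5 / √68 = 0.121 D, so the largest observed deficit that passes is 0.25 - 0.121 = 0.129 D (0.131 D at n = 70). A device whose true deficit equals the margin passes 2.5% of the time.

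**Translating the margin to the 0.5 D endpoint.** The comparator MAE is not in the documents, so 0.20 to 0.50 D is an assumption. For centred normal errors, σ = MAE / √(2/π) = MAE / 0.798, and the share within 0.5 D is 2Φ(0.5/σ) - 1. Comparing MAE with MAE + 0.25:

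| Assumed MAE (D) | Margin as % of MAE | Within 0.5 D, comparator | Within 0.5 D, at margin | Loss (points) |
|---|---|---|---|---|
| 0.20 | 125 | 95.4% | 62.5% | 32.9 |
| 0.30 | 83 | 81.6% | 53.2% | 28.5 |
| 0.40 | 62 | 68.1% | 46.1% | 22.1 |
| 0.50 | 50 | 57.5% | 40.5% | 17.0 |

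(Losses are from unrounded shares.) The largest loss under this model at any MAE is 32.9 points. For the same four MAEs, Laplace errors give 24.7, 21.4, 17.7 and 14.6 points. If the whole deficit is a constant Argos offset, the losses are 36.3, 34.3, 26.8 and 20.5, but this needs offsets of 0.44, 0.52, 0.59 and 0.65 D. The Surgery section says "Optimized lens settings will be used for each biometer", and such optimisation is ordinarily meant to remove an offset of that kind.

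**Using the plan's own SD.** For two independent centred normal errors with equal σ, the variance of the difference in absolute errors is 2σ²(1 - 2/π) = 0.727σ². Setting this to 0.5² gives σ = 0.587 and MAE = 0.798 × 0.587 = 0.468 D. The loss at the margin is then 60.6% - 42.2% = 18.4 points. Positive correlation raises the implied MAE and lowers the loss: 0.53 D and 15.7 points at r = 0.5; 0.74 D and 9.7 points at r = 0.8.

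**Matching the pass limit to a comparator error.** The 0.131 D limit holds at SD 0.5 D. With a 0.131 D deficit and independent normal errors, comparator MAEs of 0.20 and 0.30 D give a paired SD of only 0.29 and 0.40 D; of the values 0.20, 0.30 and 0.40 D, only 0.40 D reaches about 0.50 D. Its loss at that deficit is 13.4 points. A smaller SD moves the limit towards the margin (0.190 D at SD 0.25 D, 70 eyes).

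**Cost of a tighter margin.** At mean -0.05 D and SD 0.5 D, 90% power needs 119 eyes for a 0.20 D margin and 265 for 0.15 D; 70 eyes would give 70% and 38% power.

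**The case for a change.** The strongest contrary argument is that the plan's SD is probably too large, so the milder figures it implies should not reassure. Both errors come from one implanted lens and one refraction, so the difference between the absolute errors in an eye cannot exceed the gap between the two predictions. An SD of 0.5 D therefore requires a prediction gap of about 0.5 D root mean square. If the true SD and MAE are smaller, the loss at the margin moves to the upper part of the table and a larger observed deficit passes. A reason written after the refractions are known would also carry less weight than one written before.

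Much of this stands: the reason is missing, the SD has no source, and a loss of 20 to 30 points at the margin is compatible with plausible inputs. It does not show that 0.25 D is wrong, because no acceptable loss can be derived from the documents. A smaller SD leaves the test valid and only makes the trial more precise: at SD 0.40, 0.30 or 0.25 D, 68 eyes keep 90% power down to margins of about 0.21, 0.17 or 0.15 D (0.05 + 0.20 × SD / 0.5). As for timing, the value is already fixed in both the text and the SAS bound, so only its explanation could come late. The ratio of margin to planning mean carries no weight, since a margin has to exceed that mean for the trial to have power.

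**Conclusion.** No change to the plan follows. The missing rationale is a gap in explanation: the test is valid, 68 subjects at power 0.902 is correct, and the margin is prespecified. Writing down a reason would change no number, and tightening the margin without one would exchange one unexplained value for another at a cost of 119 or 265 eyes, against about 80 enrolled.

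The gap is also one that ordinary reporting fills. The lower confidence bound that decides the test, shown beside the margin, lets readers apply a stricter limit of their own. The shares of eyes within 0.5 D and 0.25 D and the median absolute error are already planned endpoints for comparing the biometers, so any loss on those scales will be visible.

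In size, a true deficit at the margin corresponds to about 17 to 33 points on the 0.5 D endpoint for an assumed MAE of 0.20 to 0.50 D with centred normal errors, and about 18 or fewer if the paired SD of 0.5 D is taken as given. MAE and error shape are assumptions. A change in mean absolute error does not by itself fix the responder loss, which could be near zero if only eyes already beyond 0.5 D worsen.
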